- 6. Social desirability bias: We will assess school staff's social desirability biases using the short form of the Marlowe-Crowne Social Desirability Scale. The short form of the scale uses 13 self-reported measures of individual characteristics, such as personality and attitudes, to understand the social desirability bias of individuals. The psychometric properties of this scale have shown it to be reliable compared to the Social Desirability Scale developed by Edwards; its use has been studied for both adolescents and adults. We will calculate the social desirability biases of each school staff member based on their responses to the measures during the baseline survey.
- **7. Existing school programs:** We will ask each staff member about their school's presence and types of bullying prevention programs, substance use prevention/treatment program, mental health prevention/treatment programs, intervention programs and policies for SGMY.

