# 9.4 Statistical Analyses

# 9.4.1 General Approach

With the ITT Analysis Population, we will calculate baseline descriptive statistics by study arm using means and standard deviations for continuous variables, and frequencies and percentages for categorical variables. We will test for differences in potential confounders between intervention and control arms using baseline staffand school-level data with Rao-Scott chi-square tests for categorical variables and linear mixed models (with a random effect for school) for continuous variables (models adjusting for the clustering of staff within schools). Secondary analyses will adjust for imbalances between arms. For previously validated scales, we will report

internal consistency via Cronbach's alpha for continuous scales. For newly created items, we will conduct exploratory factor analyses to examine the dimensions of our outcomes as well as internal consistency using baseline surveys. We will use the most recent version of Stata. All tests are two-tailed and  $\alpha$ =0.05. Given the small sample size and pilot nature of these analyses, we will not perform any corrections for multiple tests.

Regarding qualitative analyses, we will transcribe, de-identify, and quality check all data. We will perform qualitative analyses in Dedoose. We will use CFIR as a guiding framework. Two qualitative coders will independently read interviews and compare coding until they agree they are on the same page. Once the coders, we will create a final codebook with definitions, rules, and examples for each code. Two coders will then recode all data using the final codes. We will calculate inter-rater reliability (i.e., Kappa statistic) to examine code application between coders. Coders will discuss any discrepancies until they reach agreement; [name] will resolve disagreements. We will use either a qualitative descriptive coding approach (wherein we describe and count the number of code applications) or axial coding (wherein we combine inductive codes into broader categories to define emerging patterns or themes). We will identify and interpret patterns in the data using a thematic analytic approach.

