# PLANTS Pilot Trial Version 1.0 Protocol STUDY21080178 2024.04.05 Hypothesis: High school staff participants in the PLANTS arm will report pre-post improvements in active- empathic listening, self-efficacy for supporting, affirming, and protecting sexual and gender minority youths, and positive bystander intervention behaviors for bullying.

To examine the pre-post changes in high school staff outcomes, investigators will first use descriptive statistics, such as means and percentages at each timepoint within arms. To test for within-arm statistical significance, investigators will use linear mixed models for continuous outcomes and generalized linear mixed models for binary outcomes, which account for within-school and within-person clustering using random effects. Investigators will estimate the intraclass correlations for within-school and within-person effects. These models will adjust for school size (*a priori* design variable).

Hypothesis: Participants in PLANTS will report greater active-empathic listening, greater self-efficacy for supporting, affirming, and protecting SGMY, and greater positive bystander intervention behaviors for bullying in follow-up surveys than participants in the active control arm.

We will use linear mixed models for continuous outcomes and generalized linear mixed models for binary outcomes—which account for within-school and within-person clustering effects (using random effects). We will estimate the intraclass correlations for within-school and within-person effects. Regression models will include a fixed term for school size (a priori design variable), intervention group (intervention or control), time (baseline or follow-up), and the interaction of intervention group × time (our variable of interest). The test of intervention effects on secondary outcomes will be primarily based on intent-to-treat estimates. We will estimate perprotocol effects in secondary models. If there are differences in potential confounders by intervention group, we will adjust for them in secondary multivariable analyses.

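### Covariates for the secondary adjusted efficacy models are picked by between-arm baseline tests, and the form of adjustment is unstated; read as main effects, it does little about covariates that affect change

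*Combined protocol and SAP*

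**What the plan says.** Section 9.4.1 (General Approach) sets the screening step: "We will test for differences in potential confounders between intervention and control arms". It uses Rao–Scott tests for categorical items and linear models with a school random effect for continuous ones. The same section says "Secondary analyses will adjust for imbalances between arms". It also says "All tests are two-tailed and" sets α at 0.05, and it makes no correction for multiple tests.

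Section 9.4.3 describes the between-arm efficacy model: "We will use linear mixed models for continuous outcomes and generalized linear mixed models for binary outcomes", with random effects for school and person. On fixed effects: "Regression models will include a fixed term for school size (a priori design variable"), together with intervention group, "time (baseline or follow-up), and the interaction of intervention group × time (our variable of interest"). Baseline is therefore kept as an outcome, and the effect is a difference in change. The adjustment rule follows: "If there are differences in potential confounders by intervention group, we will adjust for them in secondary multivariable analyses".

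Section 9.4.7 (Sub-Group Analyses) uses another trigger: it adds variables that differ meaningfully between arms at baseline. It spells out the model terms and lists no product of those added variables with time.

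The candidate covariates are fixed baseline values. Under Section 8.1, the follow-up survey asks the demographic and social desirability items again only where they were skipped at baseline. On social desirability the baseline survey says "We will calculate the social desirability biases of each school staff member". Sections 4.1 and 6.3 name this bias as a risk of the unblinded design. Section 9.4 does not name the score.

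**The concern.** There are two separate weaknesses.

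**Selection.** A significance test between arms is a weak guide to which covariates matter. With two schools per arm it has little chance of detecting a real imbalance, while many uncorrected tests will produce chance findings. The content of the adjusted model is then unknown until the data are seen, and two sections disagree on the trigger.

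**Form.** The parameter of interest is a within-person contrast between arms. A fixed baseline covariate added as a main effect explains differences in outcome level, but that contrast has already removed them for anyone with both surveys. What it leaves open is a covariate that affects change, and a main effect does not address that.

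This matters here because schools are randomised before staff are screened and enrolled (Sections 4.1 and 6.3), so the mix of consenting staff can differ by arm. All efficacy outcomes are also unblinded self-reports. An adjusted model that can act on change is worth having, and the data for it are already collected.

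**Working it through.** **Sizes from the plan.** Section 9.2 gives 344 invited × 0.50 consenting = 172, and 172 × 0.50 = 86 per arm. Then 86 × 0.75 = 64.5, which the plan reports as 65. The stated confidence-interval widths for rates also reproduce from 2 × 1.96 × √(0.25/n): 0.106, 0.149 and 0.211 for n = 344, 172 and 86, against 0.11, 0.15 and 0.21. The plan gives no figure for the adjusted group × time analysis. Four schools give 172/4 = 43 staff per school.

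**1. Power of the screen (ICC assumed).** Take a covariate with SD 1 and a true difference of 0.5 between arms, tested on school means with 2 degrees of freedom. The variance of the arm difference, with two schools per arm, is ICC + (1 − ICC)/43. The two-sided critical value is 4.303.

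| ICC (assumed) | Variance | Standard error | Non-centrality = 0.5/SE | Power |
|---|---|---|---|---|
| 0.01 | 0.0330 | 0.182 | 2.75 | 34% |
| 0.05 | 0.0721 | 0.269 | 1.86 | 20% |
| 0.10 | 0.1209 | 0.348 | 1.44 | 14% |

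The planned mixed-model test need not use 2 degrees of freedom. A large-sample reference would raise these powers and the false-positive rate together.

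**2. Chance findings (number of covariates assumed).** For k independent tests at 0.05, the probability of at least one false flag is 1 − 0.95^k. This is 40% for k = 10, 54% for k = 15 and 64% for k = 20.

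**3. What a main effect does, continuous outcome, both surveys present.** Write the outcome of person i at time t (0 or 1) as

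Y = β₀ + s·size + a·A + τt + δ·A·t + γC + school effect + person effect + error.

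The change is D = Y₁ − Y₀ = τ + δA + (e₁ − e₀). The term γC cancels, as do the school and person effects. The estimate of δ is the difference in mean D between arms, with or without C. If C also affects change with coefficient κ, the unadjusted estimate has expectation δ + κ × (arm difference in C). A main effect leaves this as it is, whereas a C × time term removes it.

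**4. Simulation.** Set-up: 4 schools × 43 staff; true δ = 0.30; C shifted 0.5 SD between arms; effect of C on level 0.6; κ = 0 or 0.2; person and residual variances 0.5 each. All these values are assumptions. There were 15 replicates with complete data and 40 per dropout setting. Mean estimates of δ:

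| Follow-up | κ | Unadjusted | C main effect | C and C × time |
|---|---|---|---|---|
| Complete | 0 | 0.341 | 0.341 | 0.355 |
| Complete | 0.2 | 0.371 | 0.371 | 0.265 |
| 25% dropout, completely at random | 0 | 0.294 | 0.299 | 0.296 |
| 25% dropout, completely at random | 0.2 | 0.395 | 0.392 | 0.293 |
| 25% dropout, depends on C | 0 | 0.315 | 0.334 | 0.330 |
| 25% dropout, depends on C | 0.2 | 0.357 | 0.373 | 0.290 |
| 25% dropout, depends on C in opposite directions by arm | 0 | 0.417 | 0.319 | 0.314 |
| 25% dropout, depends on C in opposite directions by arm | 0.2 | 0.604 | 0.495 | 0.343 |

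With complete data and κ = 0, the shift from adding the main effect was 0.000000 and the standard error was 0.1503 both ways, while the arm main effect moved from 0.298 to −0.017. Theory for κ = 0.2 gives 0.30 + 0.2 × 0.5 = 0.40 unadjusted. The simulated 0.371 is within its Monte Carlo error of about 0.154/√15 = 0.04. Under completely random dropout the mean shift from a main effect stayed within 0.005, with a largest single shift of 0.067.

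**5. Binary outcome.** A random-intercept logistic model (person effect only, 60 replicates per setting) gave mean shifts in the log-odds interaction of 0.0002 with complete data (largest 0.055) and 0.010 with 25% random dropout (largest 0.214).

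**The case against.** A reader might infer that the adjusted models cannot change the effect at all, so that reporting them would be empty reassurance. The documents do not support that reading, for five reasons.

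- **Form.** No section says that covariates enter as main effects only. It is the natural reading of the adjustment sentence, and the term list in Section 9.4.7 supports it, but that list belongs to the subgroup models. The documented gap is an unstated form.
- **Dropout.** Section 9.3 defines the intention-to-treat population as all enrolled staff, and Sections 9.1 and 9.2 allow for about 25% loss, so staff with one survey will be in the model. Sections 4.1 and 6.3 name attrition bias as a risk. When dropout depended on the covariate in opposite directions by arm and the covariate affected level only, a main effect moved the mean estimate from 0.417 to 0.319 (truth 0.30) and removed most of the bias.
- **Binary outcomes.** The exact cancellation is a property of the linear model. Individual logistic estimates did move.
- **Level imbalance.** Where the estimate does not move, this is partly because level differences already cancel within person. That is a strength of the design.
- **Reporting.** No section plans a claim of robustness from these models.

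Two smaller points also stand. The social desirability score is baseline staff data, so the screen could pick it up; it is unnamed, not excluded. Section 9.4.7 already fits role in school with all two-way terms, hence role × time, though to study effect modification and not to give an adjusted overall estimate.

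None of this rescues the selection rule, and none of it shows that the adjustment would reach covariates that affect change.

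**Conclusion.** The point holds in a limited form. Selection by between-arm tests is weak: 14% to 34% power for a 0.5 SD imbalance, and a 40% to 64% chance of at least one false flag. These figures rest on the assumed ICCs, the 2-degree-of-freedom approximation, and 10 to 20 independent candidates. The trigger also differs between Sections 9.4.3 and 9.4.7.

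The form of adjustment is not stated. On the main-effect reading, a zero shift for continuous outcomes with complete pairs is algebra and needs no assumption about effect sizes. The near-zero average shift under completely random dropout, and the useful shift of about −0.10 under arm-dependent dropout, come from the simulation settings. The gain from adding covariate × time depends on the assumed effect on change of 0.2, for which the documents give no value.

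The consequence is modest. The primary endpoints are descriptive and use the PLANTS arm only (Section 9.4.2), and the main intention-to-treat efficacy estimate does not depend on this step. It is a cheap improvement to secondary models of secondary endpoints.

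**What to change.** In Sections 9.4.1 and 9.4.3, drop the between-arm tests as the rule for choosing covariates, and present baseline characteristics by arm descriptively. Name in advance a short list of staff-level baseline covariates already collected under Section 8.1, for example the social desirability score, previous professional development on working with SGMY, and role in school (in a few groups fixed in advance).

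State the form of the secondary adjusted model as one of:

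- the planned mixed model with each covariate entered together with its interaction with time; or
- a model for the follow-up score, adjusted for the baseline score and these covariates, with the school random effect kept. This version uses only staff with a follow-up score.

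Use the same covariate list in Section 9.4.7 in place of its separate trigger.

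The cost is SAP wording and a few staff-level degrees of freedom. No new data are needed, and the main unadjusted intention-to-treat model stays as planned.

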### Additional Analyses

Participant bias assessment will compare staff participants' demographics (at baseline) to publicly available school-level data. We will report significant differences as potential validity threats.

Attrition bias assessment will compare staff respondents who completed follow-up surveys versus those who did not by baseline demographics and outcomes.

# 9.4.4 Safety Analyses

Hypothesis: High school staff in the PLANTS arm will have low adverse event prevalence (≤20% of PLANTS participants will report adverse events).

We will estimate the prevalence of adverse events by calculating the percentage and 95% confidence interval of school staff that reported adverse events experienced any time after PLANTS deployment and use.

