#### 8.2 Safety Assessments

In each staff survey, we will assess the following variables. In addition to the questions below, we will also leave open-ended text boxes so people can provide more detail on the incident.

Variables	Description	Levels/range	Justification
Parent backlash	Contact from disgruntled parents/guardians of students because LGBTQ+ inclusivity is in the classroom	Yes/no + Frequency	Parents may not be comfortable with the education their children are receiving and ask questions that educators may not be comfortable or feel safe answering.
	People attack school staff or the school for supporting LGBTQ+ youth	Yes/no + Frequency	This is happening all over the country
School board backlash	School board gets upset or concerned about staff supporting LGBTQ+ youth	Yes/no + Frequency	This is happening all over the country
Suspension or removal from employment	•	Yes/no + Frequency	This is happening all over the country

PLANTS Pilot Trial Protocol STUDY21080	178		Version 1.0 2024.04.05
Censorship of	Promotion and integration of	Yes/no +	This is happening throughout the
-	LGBTQ+ issues, history,	frequency/quantity	country
literature/history/stories	stories into the school		
or removal of books	curriculum could lead to		
with LGBTQ+	attempts to censor that		
	information by parents, school		
	boards, and higher ups in the		
	education system. Oftentimes		
	this has been justified as		
	avoiding "controversial/political		
	topics" in schools. There is the		
	possibility that teachers who		
	teach about		
	"controversial/political" topics		
	could be silenced via threats of		
	losing their jobs.		
Emotional discomfort	Staff are uncomfortable with	Likert 5-point	Some topics may provoke
with PLANTS	the training program.	scale + Open-	discomfort.
		ended	

Study team members will have contact staff and will be able to report adverse events in the appropriate case report form. In the post-trial interviews, we will interview a subset of participants who reported experiencing adverse events. We will ask questions about the AE during interviews, which will help support knowledge of the study intervention effects. We will follow-up with individuals if the event is severe (see the MOP).

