# Secondary Endpoints

We anticipate inviting at least 344 school staff to participate in the pilot study, and assuming 5% type I error rate, we will be able to estimate a 95% confidence interval width of no more than 0.11 for the participation rate. Assuming a participation rate of 50% (n=172), we will be able to estimate a 95% confidence interval width of no more than 0.15 for the attrition rate. Assuming half of the consenting participants are in the intervention arm (n=86), we will be able to estimate 95% confidence interval widths of no more than 0.21 for the proportion of school staff who adhere to the PLANTS intervention and for the proportion of school staff who report adverse events.

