#### Additional Analyses

We will report overall frequency (adding together all the adverse events reported) of adverse events by study arm, followed by the frequency of all types of adverse events by study arm. We will also report the total number of adverse events by severity and average duration, overall and by arm. We will also examine the frequency and percentage of school staff reporting adverse events (which will be counted once only for a given participant). We will also calculate adverse events by school level. We will report study arm-specific percentages of schools that had staff who reported any adverse event and by each type of adverse event.

Study arms will be compared on baseline characteristics (e.g., demographics) using descriptive statistics. We will test for differences in potential confounders between intervention and control arms using baseline staffand school-level data with Rao-Scott chi-square tests for categorical variables and linear mixed models (with a random effect for school) for continuous variables (models adjusting for the clustering of staff within schools).

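### The only safety benchmark (at most 20% of PLANTS staff reporting an adverse event) ignores the EMAILS arm, and it is a loose ceiling if incidence is low, as the plan expects

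*Combined protocol and SAP*

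**What the plan says.** Section 3 sets determining the safety of PLANTS as a secondary objective and lists five event types: parent, social media and school board backlash, job action, and censorship. The only safety hypothesis is in section 9.1 and again in 9.4.4: "High school staff in the PLANTS arm will have low adverse event prevalence (≤20% of PLANTS participants will report adverse events". The analysis sentence that follows it in 9.4.4 begins "We will estimate the prevalence of adverse events by calculating the percentage and 95% confidence interval of school staff that reported adverse events", and it counts events arising at any point once PLANTS is in use.

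Section 8.2 adds a sixth item, emotional discomfort with the PLANTS training. It justifies the items on attacks on staff or school, school board backlash and job action with "This is happening all over the country", and says nearly the same of censorship. Parent backlash and emotional discomfort have other justifications. On collection it says: "In each staff survey, we will assess the following variables". The schedule in section 1.3 marks adverse-event reporting at baseline, during both programmes and at follow-up.

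The Additional Analyses under 9.4.4 begin: "We will report overall frequency (adding together all the adverse events reported) of adverse events by study arm". They go on to event types, severity, average duration and the percentage of schools affected by arm. The percentage of staff reporting an event, each counted once, is also planned, but that sentence does not say by arm.

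**The concern.** Whether the 20% figure is met depends only on the total event rate among PLANTS staff. That total mixes events the course provoked with events that would have happened anyway. The protocol itself says that most of these event types occur nationally. Schools are randomised 1:1 and the shared items are asked in both arms, yet the safety hypothesis does not use the comparator. For efficacy, section 9.4.3 models arm, time and their interaction.

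At stake is the safety message carried into the fully powered trial that section 2.1 says this pilot will inform. If the background is low, a several-fold increase can sit under 20% and be reported as consistent with the safety hypothesis. If the background is high, a course that adds nothing can exceed 20%.

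**Working it through.** **Inputs from the plan.** The benchmark is 20%. Section 9.2 plans this proportion on n=86 PLANTS staff (344 × 0.5 × 0.5). With 75% completing follow-up, 86 × 0.75 = 64.5, which the plan rounds to 65. There are four schools, two per arm.

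**Inputs assumed.** The documents give no background rate and no ICC for these events. Rates of 5% to 30% and ICCs of 0 to 0.20 are assumptions.

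**The plan's own figure.** Section 9.2 states "95% confidence interval widths of no more than 0.21". The Wald width at p = 0.5 is 2 × 1.96 × √(0.5 × 0.5 / 86) = 0.211, so it reproduces. It describes the precision of one percentage and does not bear on what that percentage means.

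**Chance that the observed percentage is at most 20%.** Since 0.20 × 65 = 13 and 0.20 × 86 = 17.2, the benchmark is met with at most 13 of 65 or 17 of 86 staff reporting. For independent staff, P(met) = Σ C(n,x) pˣ(1−p)ⁿ⁻ˣ for x from 0 to 13 or 17. For two schools, each school's rate is drawn from a beta distribution with parameters p(1/ICC − 1) and (1 − p)(1/ICC − 1).

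| True PLANTS rate | n=65, independent | n=86, independent | n=65, ICC 0.05 / 0.20 | n=86, ICC 0.05 / 0.20 |
|---|---|---|---|---|
| 10% | 0.996 | 0.998 | 0.95 / 0.86 | 0.95 / 0.85 |
| 15% | 0.90 | 0.91 | 0.80 / 0.73 | 0.79 / 0.72 |
| 20% | 0.57 | 0.54 | 0.57 / 0.58 | 0.55 / 0.57 |
| 25% | 0.22 | 0.16 | 0.33 / 0.44 | 0.30 / 0.42 |
| 30% | 0.05 | 0.02 | 0.16 / 0.31 | 0.13 / 0.29 |

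*Course adds events.* If a 5% background is tripled to 15%, the benchmark is met with probability 0.90 or 0.91 under independence, and 0.72 to 0.80 with clustering. If 5% is doubled to 10%, it is met with probability above 0.99 under independence, and 0.85 to 0.95 with clustering.

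*Course adds nothing.* The true rate then equals the background. At n=65 with independence, the probability of exceeding 20% is 0.004 at a 10% background, 0.10 at 15%, 0.43 at 20% and 0.78 at 25%. With clustering, the 25% figure falls to 0.67 (ICC 0.05) or 0.56 (ICC 0.20).

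**What a between-arm estimate would show.** With 5% in EMAILS and 15% in PLANTS, n=86 per arm, the difference is 0.10. Its standard error is √((0.05 × 0.95 + 0.15 × 0.85)/86) = 0.045, so the 95% CI is 0.01 to 0.19 under independence. At ICC 0.05 the design effect is 1 + 42 × 0.05 = 3.10 and the interval is −0.06 to 0.26. With 25% in both arms the difference is 0, with interval −0.13 to 0.13, or −0.23 to 0.23 at ICC 0.05. These are normal approximations and too narrow with two schools per arm. The estimate is imprecise, but it tells the two situations apart in direction, which the single-arm percentage cannot do.

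**The case against.** The strongest reply is that much of this is already planned. The Additional Analyses give event counts, types, severity, duration and schools affected by arm, so a reader will see EMAILS events beside PLANTS events. That stands, and it narrows the gap to three things: the once-per-person percentage by arm, a difference, and a link from these tables to the safety statement.

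A reader might infer that 20% is a pass/fail decision rule. The documents do not support that. Section 9.4.4 says the prevalence will be estimated, and neither the suspension and termination grounds in section 9.5 nor any progression criterion refers to 20%.

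A reader might also infer that ordinary background backlash is likely to condemn a harmless course. That needs a background near or above 20%. The documents give no rate, section 2.3.3 calls backlash unlikely, and section 3 anticipates low incidence.

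The plan does have safeguards: section 8.3.4 excludes events present at screening and 8.3.3.2 grades relatedness. Both help interpretation. Neither enters the 20% figure, new background events still count, and an event can be graded related on timing alone.

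Finally, the comparator is imperfect. EMAILS covers similar topics and its resources also go to PLANTS staff, so the difference can miss harm common to both arms. Reporting is unblinded, and section 6.3 itself names bias in reporting adverse events. No recall period is given for the baseline items. All of this stands, and it limits how the difference can be read. It does not make the single-arm percentage easier to interpret.

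**Conclusion.** The point holds in a limited form. The only safety hypothesis judges PLANTS on its own total event rate, and the by-arm description already planned is not connected to that judgement. The size of the problem depends on a background rate the documents do not give. Under their expectation of low incidence, 20% is a loose ceiling: a tripling from 5% to 15% would meet it about nine times in ten if staff are independent, and roughly seven to eight times in ten with two schools and an ICC of 0.05 to 0.20. Clustering is the more realistic case, because school board action, attacks on the school or book removal would be reported by many colleagues at once. The opposite error is secondary and becomes the usual result only at a background above about 20%. The change should be made, but this is a matter of how a secondary objective is stated and not a flaw in the trial's primary aim.

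**What to change.** In sections 9.1 and 9.4.4:

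- Report the percentage of staff with at least one of the five shared event types in section 3, after programme start, for PLANTS and for EMAILS. Give the PLANTS minus EMAILS difference and each school's figures. Label this a descriptive estimate, not a test, and base the safety statement on it.
- Keep 20% as a flag, read beside the EMAILS rate and the related/not related grading.
- Leave the item on emotional discomfort with PLANTS out of the between-arm comparison, because it is specific to one arm. Report it for PLANTS alone.
- Show baseline percentages as context only if their recall period matches follow-up.
- State that the difference measures PLANTS-specific excess over EMAILS, not excess over no training, and that reporting is unblinded.

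The cost is SAP wording and one table from data already planned for collection. The downside is a less categorical safety statement, because two schools per arm leave the difference imprecise.
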